The gross under-diagnosis of hypertension and diabetes suggests that improving awareness of risk factors is central to reducing CVD morbidity and mortality. Inadequate medication of these conditions is likely attributable, in large part, to lack of availability and affordability of medicines. But it could also stem from under appreciation of the risks of untreated, asymptomatic conditions, as well as the effectiveness of pharmacotherapies in preventing the progression from risk factor exposure to disease. Lack of appreciation of the long term gains from treating a condition that does not currently cause discomfort likely contributes to poor adherence to medication and lack of control of hypertension.

Central to these explanations for low awareness, medication and control of hypertension, diabetes and other CVD risk factors are beliefs about susceptibility to health risks, severity of consequent health conditions and effectiveness of medication in containing illness. According to the *health beliefs model* (Rosenstock 1966) providing individuals with information on their risk of developing CVD and counselling on actions to avert or manage the risk will lead to adoption of healthier lifestyles and uptake of effective screening and medication. But this may be overly simplistic. Without sufficient knowledge of the epidemiology of CVD, behaviour may change little in response to information about exposure to risk factors that do not immediately manifest in health problems. A negative result from a screening test could even encourage unhealthy habits that take time to have physiological effects. Bad news from a screening test that the risk is higher than had been anticipated may be filtered out by optimistically biased individuals wishing to avoid the distress aroused by contemplation of life-threatening disease (Sharot & Garrett 2016). Understanding how individuals respond to information on CVD risks is critical to designing programs that are effective in managing those risks.

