- Rather, a *randomized encouragement design* is adopted in which respondents in randomly selected barangays will be offered the opportunity to enter a lottery for a money prize on condition of attending a RHU/CHC for a checkup within a month. The lottery will have a selection probability of 10% and a prize of 5,000 PHP. There will be one lottery within each of the selected barangays.

- The offer of a lottery ticket will be used to instrument presentation for checkup at RHU/CHC allowing the effect of the latter on predicted 10-year CVD risk, plus risk factors (smoking, BMI, blood pressure), hypertension diagnosis and medication at follow-up to be identified.
- Specifically, we will estimate the regression model,

$$Y_{it} = \gamma Y_{it-1} + \beta x_{it-1} + \tau \,\hat{s_i} + \mu_{it} \tag{6.1}$$

where Y_{it} represents the outcome variable (e.g. predicted CVD risk) at follow-up and \hat{s}_i is the predicted value of a binary variable that equals one for those who attended a RHU/CHC for a checkup, and zero otherwise. The prediction is obtained from the first stage regression described in [H6b] that makes use of the random offer of entry to the lottery. Y_{it-1} and x_{it-1} are the outcome and covariates respectively at baseline. Note that only individuals that are either in the lottery incentive group or in the control group are used for this regression.

• The instrumental variable estimate of τ is an estimate of the impact of a RHU/CHC checkup on the outcome for those induced to present for checkup by the lottery offer who would not have presented for a checkup otherwise.

[H6b] The lottery offer is a strong instrument for presentation at a RHU/CHC for a checkup.

Test:

• Using both the treated respondents who are offered the lottery prize and the control respondents who are not, we will regress a binary variable indicating RHU/CHC attendance (s_i) on a binary variable indicating whether or not the lottery prize was offered (L_i) , i.e.

$$s_i = \gamma Y_{it-1} + \beta x_{it-1} + \kappa L_i + u_i.$$
(6.2)

 $\hat{\kappa} > 0$ indicates that the lottery offer raises attendance. We will test for weakness of the instrument.

[H6c] Individuals who have a preference for risk respond more to the offer of a lottery prize. Thus, the intervention has a larger effect on individuals who potentially engage most in lifestyles that bring exposure to CVD risk.

Elaboration

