5.3 Lottery incentive for CVD risk assessment

The goal of the second intervention is to evaluate the effectiveness of the PhilPEN program in delivering primary prevention of CVD. This will be achieved by offering randomly selected respondents a ticket for a lottery with a money prize on condition that they visit a RHU/CHC for a checkup. There will be one prize per barangay giving each respondent a one in ten chances of winning P5000 (US\$100). The prize is equivalent to approximately 14 days earnings at the regional minimum wage⁵. This *randomized encouragement design* will induce exogenous variation in patients accessing the PhilPEN program allowing its impact to be estimated.

As noted in Section 3.1, there are potential weaknesses in implementation of the PhilPEN program and the purpose of this component of the experiment is to establish the effectiveness of the program as it is currently implemented. For that reason, there is no supply-side component to the intervention. Respondents will simply be told that they can enter a lottery if they go to the RHU/CHC for a checkup. The health facilities will be told to conduct an assessment deemed appropriate for any particular patient that requests to be issued with a lottery ticket. No instructions will be given that the facilities should follow the PhilPEN protocol. We will evaluate whether they do implement the protocol for patients who qualify (by age if nothing else) for full risk screening.

The remainder of this sub-section describes the logistics of the lottery intervention.

Designating a RHU/CHC point person. The agreement will state that the MHO/CHO should designate a point person in the RHU/CHC facility who will be responsible for handing out the lottery tickets. This should be one of the medical staff (e.g. the rural health nurse, midwife or the MHO/CHO, or PhilPEN coordinator) who performs or delegates the performance of the PhilPEN profiling and screening. The identity of this point person will be included in the information provided by enumerators to the lottery recipients.

Voucher and ticket. A voucher will be given by the enumerator to those deemed eligible for the lottery intervention at the end of the interview. This voucher will be surrendered at the facility to the RHU/CHC point person in exchange for a lottery ticket. The voucher and ticket will both be pre-numbered with the same number.

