The information will be recorded on the detachable portion of the lottery ticket (similar to the usual raffle tickets) so that it looks authentic. The point person will then collect the voucher, release the lottery ticket with the same number as that on the voucher and have the recipient sign a receipt. We will leave it to the point person to convince the lottery voucher recipient to undergo any assessment deemed appropriate and to release the ticket afterwards.

UPecon recording of who went to the clinic. Part of the tasks of the RHU/CHC point person is to collate information on who among the voucher recipients have gone to the clinic to claim their tickets. We will request the point person to text a designated number (UPecon hotline) with the name, age, voucher and ticket number that have been claimed, and the contact details of the recipient, immediately after the lottery ticket has been claimed (at the end of each day). After the designated time period allowed to claim tickets, the UPecon R4D team will collect the ticket stubs and vouchers from the RHU/CHC point person.

Lottery draw. The UPecon Team will be responsible for drawing the lottery winners. During the ticket claiming period, the UPecon team will update the list of respondents who have claimed their tickets based on the SMS and email messages of the RHU/CHC point persons. The UPecon team will validate this with the list of voucher recipients submitted by the survey team. Matching voucher and ticket numbers will be included in the list of lottery entries. Once the claim period for the tickets has passed, one week will be allowed for all the claimed ticket numbers to be transmitted to the UPecon team and for all ticket stubs and vouchers to be collected from the RHU/CHCs by the UPecon team. One winner will be drawn from each barangay included in the lottery intervention. If there are no claimants of the lottery tickets from the particular barangay, no winner will be drawn. Once the winners are drawn, an SMS message will be sent to the respondent informing them that they have won and for them to expect a message as to how the prize can be claimed. They will also be informed to designate a representative should they not be available to receive the prize.

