- c. *Prize administration*. The UPecon study team will be in charge of remitting the prize money to the winners. The UPecon team will tag these winners and encode an indicator in the survey data.

Additional security measures will be developed to:

- a. ensure against duplication of vouchers and tickets
- b. ensure against a non-respondent claiming the tickets at the facility
- c. ensure against a non-winner receiving the prize
- d. stipulate protocol in case of voucher and ticket loss

Additional expenses (To follow based on decisions).

- e. Fees for hotline (prepaid plan?)
- f. Data plan for CHC/RHU point persons?
- g. Fees for delivery of prize money (usually % of prize money)
- h. Token to RHU/CHC point person to defray the incidental cost for managing the lottery?

6. Timeline

A baseline survey will serve two purposes. First, it will identify respondents eligible for the interventions within the randomly selected barangays and will be the point at which the interventions are delivered. Second, while the impact of the interventions will be identified by comparison between each randomly selected treatment group and the control group post intervention, data collected on outcomes and covariates at baseline will be used to increase power.

Table 2: Timeline

Activity					2017							20)18		
-	Apr	May	Jun	Jul	Aug	Sep	Oct	Nov	Dec	Jan	Feb	Mar	Apr	May	Jun
UPecon IRB approval	Х														
Canton de Vaud Ethics			Х												
Committee approval															
Field mobilization		Х	Х	Х											
Contracting survey firm		Х	Х	Х											
Translation &			Х	Х											
programming of															
questionnaire															
Pre-test and questionnaire			Х	Х											
revision															
Train enumerators			Х	Х											
Field baseline survey					Х	Х									
UPecon survey					Х	Х									
monitoring															
Survey firm delivers						Х	Х								
baseline data															
Progress report to FSNSF-				Х											
SDC															
Analysis of baseline data								Х	Х	•••	••				
Draft paper from baseline										Х	Х				
analysis															

Activity					2017							20)18		
	Apr	May	Jun	Jul	Aug	Sep	Oct	Nov	Dec	Jan	Feb	Mar	Apr	May	Jun
Track respondents										Х					
Workshop on baseline									Х						
results															
Draft follow-up									Х						
questionnaire															
Pre-test and questionnaire										Х					
revision															
Train enumerators											Х				
Field follow-up survey												Х	Х		

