UPecon survey												Х	Х		
monitoring															
Survey firm delivers														Х	
follow-up data															
Analysis of follow-up data														Х	Х
Write papers															\rightarrow

Our intention is to field the baseline survey in August-September 2017. As explained above, the information intervention will form part of the risk perceptions module of the baseline survey. The module used with information treatment group respondents will differ from that used with the lottery treatment group and the control group. The module will be positioned in the survey after physical measurements of blood pressure and BMI in order that these measures can be used in the calculation of the predicted CVD risk that will be revealed to the treatment group respondents.

Those allocated to the lottery intervention will be told of their chance to enter the lottery at the end of the baseline survey and given a voucher to be exchanged for a lottery ticket at a specific RHU/CHC. The chance to enter the lottery expires one month after the baseline in order that we observe a sufficiently long period between risk assessment at the designated facility and the follow-up survey.

The follow-up will be conducted around 6-7 months after the baseline in March-April 2018. This will provide sufficient time to observe the effect of medications prescribed at initial contact with the RHU/CHC and to assess whether follow-up consultations are conducted for the target populations, as stipulated by the PhilPEN protocol.

7. Outcomes

We will estimate effects on predicted CVD risk, risk factors, health care management of CVD, CVD-related behaviours, perceptions of CVD risk and knowledge of CVD risk factors.

Principal outcome

The principal outcome for both interventions is mean 10-year risk of a heart attack or stroke predicted using the office version of Globorisk (Udea et al 2017).

i) Mean 10-year risk of CVD event (Globorisk prediction)

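### Model (6.1) credits the whole effect of the lottery offer to the checkup, although about 1 in 10 of the lottery arm also receives 5,000 PHP; the recorded winner tag allows a cheap check that the plan does not include

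*Combined protocol and SAP*

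**What the plan says.** Section 3.2, [H6a]: "The offer of a lottery ticket will be used to instrument presentation for checkup at RHU/CHC". Equation (6.1) regresses the follow-up outcome on predicted attendance, and its coefficient is interpreted as the effect of the checkup on those whom the offer induces to attend. The elaboration of [H6c] calls it the effect of PhilPEN on compliers.

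The prize:
- Section 3.2: "The lottery will have a selection probability of 10% and a prize of 5,000 PHP".
- Section 5.3: "One winner will be drawn from each barangay included in the lottery intervention". The draw is among people who claimed a ticket: "If there are no claimants of the lottery tickets from the particular barangay, no winner will be drawn".
- Section 5.3: "The prize is equivalent to approximately 14 days earnings at the regional minimum wage".
- Section 6: "The chance to enter the lottery expires one month after the baseline". Section 5.3 puts the draw one week after the claim period, and section 6 puts follow-up 6-7 months after baseline.
- Section 5.3, on prize administration: "The UPecon team will tag these winners and encode an indicator in the survey data".

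Equations (6.1) to (6.4) have no winner term, and no analysis of the tag is described. [H6a] declines to use the information arm as an instrument because beliefs could alter behaviour without any contact with a facility. The same question is not asked of the prize money. The defence of identification at the end of section 10.2 covers only changes in how facilities behave.

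**The concern.** An instrument identifies the effect of the checkup only if the offer has no other route to the outcome. Cash to one claimant per barangay is another route, and the plan's own account of the setting makes it plausible. Section 2 says the province was chosen for its relatively high poverty and that drug deliveries can be late or stocks run out. Section 3.1 states: "Inadequate medication of these conditions is likely attributable, in large part, to lack of availability and affordability of medicines". The money could help winners pay for medicines or travel, or could go on tobacco. A direct effect could therefore have either sign.

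The second objective is whether PhilPEN, as implemented, works. If the prize moves smoking, BMI, blood pressure or medication, (6.1) reports that movement as an effect of PhilPEN, and nothing in the planned output would reveal it.

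**Working it through.** **Inputs.** 80% power, 5% significance, effect 0.2 SD (section 10.1); ICC 0.1, 10 per cluster at follow-up, correlation with baseline 0.6, attrition 10%, compliance 60% or 50% (section 10.1, Table 4); arm sizes (Table 6). I assume a two-sided test, and I use 60% both as ticket take-up and as the first-stage difference.

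**1. The plan's sample size.** n = 2[SD(1.960 + 0.842)/difference]² × (1 - 0.36) × (1 + 9 × 0.1). For CVD risk, SD = 11.35/5 = 2.27 and the difference is 11.35 - 10.89 = 0.46, so n = 464.8. That is 47 clusters, and 470/0.6² = 1,306, as in Table 6. The 1,361 for binary outcomes equals 490/0.36, that is, 49 clusters before the compliance adjustment.

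**2. Share of the arm that wins.** 1,361/10 gives about 136 barangays and so about 136 winners, 10% of the arm. Before attrition there are 10/0.9 = 11.1 people per barangay, which gives 9%. Among claimants the chance is 1/(10 × 0.6), about 1 in 6.

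**3. Timing.** 6 to 7 months less one month and one week is 4.8 to 5.8 months from draw to follow-up.

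**4. Shift in the complier estimate.** With x the mean effect of winning among winners, shift = (share winning × x)/first stage.
- 60% compliance: 0.10x/0.6 = x/6 (0.09x/0.6 = 0.15x with the 9% share).
- 50% compliance: 0.10x/0.5 = x/5.

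The documents give no x. For assumed values at 60% compliance:

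| Assumed x (SD) | Shift (SD) | Share of 0.2 SD | Rejection rate if the checkup has no effect (nominal 5%) |
|---|---|---|---|
| 0.1 | 0.017 | 8% | 5.6% |
| 0.2 | 0.033 | 17% | 7.6% |
| 0.3 | 0.050 | 25% | 10.9% |
| 0.5 | 0.083 | 42% | 21.9% |

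The last column uses SE = √(2/1361 × 0.64 × 1.9) = 0.0423 SD for the arm difference and a displacement of 0.10x. The shift equals the whole 0.2 SD only if x = 1.2 SD.

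**5. Why reweighting works.** The winner is drawn at random from the n claimants in a barangay, so each claimant escapes the prize with probability (n-1)/n. Weighting non-winners by n/(n-1) restores the claimants' share. With 6 claimants of 10, removing the winner without weights lowers observed attendance to 5/9 = 56%; with weight 1.2 it is 5 × 1.2/10 = 60% again. A winner dummy in (6.1) is no substitute, because only attendees can win and the dummy conditions on attendance.

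**6. Cost in precision.** Effective n per cluster = 10²/(5 × 1.2² + 4) = 100/11.2 = 8.9. The variance ratio for the arm mean is (0.1 + 0.9/8.93)/(0.1 + 0.9/10) = 1.057. Unweighted with 9 per cluster it is 1.053. Hence 5-6%.

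**7. Precision of the cash effect.** Winners against non-winning claimants within barangay: 1,361 × 0.6 = 817 claimants, 136 winners and 681 others. SE = √[0.64 × 0.9 × (1/136 + 1/681)] = 0.071 SD, so the 95% half-width is 0.14 SD. Divided by 6, that is 0.023 SD on the IV scale.

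**The case against.** - **The size is unknown and may be small.** This stands. Large values look strained for medication: Table 5 has 31% with systolic pressure of 140 or more, so a 20-point rise in antihypertensive use among winners would mean that cash alone started treatment in about 0.20/0.31, or two-thirds, of those with raised pressure. That x would add 20/6 = 3.3 points, against the planned 6 (0.10 to 0.16); a 5-point x would add 0.8.
- **Cash may not be the binding constraint.** Section 2 says the supply programmes are meant to provide antihypertensives free at RHU/CHCs. Statins are unsupplied, but cholesterol does not enter office-based Globorisk, so statins cannot move the principal outcome through that input. This narrows the medication route to stock-outs and private purchase; smoking, diet and weight remain.
- **Winners have all attended.** Drugs bought after a new diagnosis partly reflect the checkup. This stands, and the winner contrast would then estimate the effect of money given attendance.
- **Division by compliance makes it worse.** A reader might infer this. Moving from the arm difference to the complier scale enlarges signal and bias equally, so the scaling adds no harm. Lower compliance does raise the bias relative to the signal, because the number of prizes per barangay is fixed.
- **The stated odds could mean 10% per claimant.** Winners would then be 6% of the arm and the shift 0.06x/0.6 = 0.10x. The draw procedure is the more specific text and gives x/6.
- **Any paid encouragement has an income path.** True. A lottery confines the cash to a few people and randomises it among claimants, which is why it can be checked here.

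**Conclusion.** The exclusion restriction behind (6.1) is open on one identifiable route, and the plan is silent on it. The possible shift is about x/6 of the effect of winning (0.10x to x/5 across the readings and compliance rates above): modest unless winning has a large effect, and zero if it has none. Its sign is not known either.

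A reader might infer that the PhilPEN estimate will be biased, or that the design fails. The documents do not support that: they contain no estimate of what the money does, and the SD values above are assumptions. What they support is that an assumption essential to the second objective goes untested when the data to test it will already be held. This is a worthwhile, inexpensive improvement to the analysis plan.

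The figures rest on one winner per barangay, 60% compliance, 10 people per cluster and the plan's ICC and baseline correlation. The correction also needs loss to follow-up to be unrelated to winning.

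**What to change.** Add to [H6a]:

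1. Keep (6.1) as the main estimate.
2. Pre-specify a sensitivity analysis that re-estimates both stages, (6.2) and (6.1), with winners removed and the remaining claimants in each barangay weighted by n/(n-1). Here n counts all claimants in that barangay, including those later lost. State the assumption that loss to follow-up is unrelated to winning, and report follow-up rates for winners and non-winning claimants.
3. Report the winner versus non-winner contrast among claimants within barangay, with its interval, as the direct randomised estimate of the cash effect. Expect about ±0.14 SD, or ±0.023 SD on the IV scale. That bounds the problem but cannot exclude a small cash effect.
4. If the PhilPEN conclusion from (6.1) does not hold in the winner-excluded analysis, qualify it. Do not let the headline estimate switch according to how far the two differ, since that would be a data-dependent choice.
5. Say how a barangay with a single claimant is handled, since n/(n-1) is undefined there. With 11 people at 60% take-up the probability is 11 × 0.6 × 0.4¹⁰ = 0.0007 per barangay.

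The change is to analysis wording only; the winner indicator is already to be recorded. The sensitivity analysis carries about 5-6% more variance in the lottery-arm mean, and the main analysis loses nothing.
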